8.3.8. Pregnancy Testing

- WOCBP (Section 10.4.1) will be tested for pregnancy by serum at screening. Urine tests for pregnancy will occur at the time points specified in the SoA (Section 1.3).
- Pregnancy testing in WOCBP will be conducted at the end of relevant systemic exposure (ie, at the safety follow-up visits).
- Additional pregnancy testing may be performed as necessary by the investigator or as required by local regulations, to establish the absence of pregnancy at any time during the study.
- Any pregnancy reported during a clinical research study, including the safety follow-up period, is routinely monitored as standard practice. The pregnancy could have arisen from a female clinical study participant or a male participant's female partner. In either situation, consent will be requested to collect medical information about the pregnancy and the baby's health for up to 12 months after the baby's birth.

8.3.9. Additional Safety Assessment – the Glucocorticoid Toxicity Index

As an additional assessment of the impact of glucocorticoid morbidity, the GTI v2.0 will be assessed at the visits listed in the SoA (Table 1). The GTI v2.0 is a complementary scoring system to the overall report of AEs that are considered related to glucocorticoids by investigators during interventional studies. It also enables the monitoring of long-term tolerability of glucocorticoids during their prolonged use during clinical practice.³⁹

The GTI v2.0 consists of the following 2 instruments:

The Composite-GTI (C-GTI), which serves as a primary instrument intended to capture
toxicities that are likely due to glucocorticoid exposure. The C-GTI has 9 functional
domains: BMI, glucose control, blood pressure, lipid metabolism, bone mineral density,
muscle strength, skin toxicity, neuropsychiatric effects, and infection. Each domain
includes several weighted items that correspond to varying degrees of glucocorticoid
toxicity.

Note: the bone mineral density domain will not be used in this study, because it is typically excluded from studies <1 year in duration, because bone densitometry is not sufficiently reliable in measuring changes over shorter durations.³⁹

Two analytical scores are generated from the weighted C-GTI items: the Cumulative Worsening Score (CWS) and the AIS. The CWS is designed to assess cumulative glucocorticoid toxicity, while the AIS can be used to assess whether a new therapy is effective in reducing glucocorticoid toxicity over time. Together, the CWS and AIS provide complementary information about the ability of an investigational agent to reduce overall glucocorticoid toxicity.

• The Specific List of the GTI (GTI-SL) captures well-known glucocorticoid-related side effects. This non-weighted instrument provides additional information for the domains

most affected by glucocorticoid use during the participant's course of treatment. It comprises 11 domains (9 of which are shared in common with the C-GTI) and 23 items.

Note: for the reason mentioned above, the GTI-SL item covering bone mineral density decrease (part of the Bone Health domain; Table 15) will not be used in this study.

The tabular components of the modified GTI are presented in Section 10.12.

8.4. Adverse Events, Serious Adverse Events, and Other Safety Reporting

The definitions of AE and SAE are provided in Appendix 3 (Section 10.3). An AESI is an AE of scientific and medical concern specific to the sponsor's product or program and described in Section 8.4.7.

AEs (including SAEs, AESIs, and AEs of clinical interest) will be reported by the participant (or, if appropriate, by the caregiver or surrogate).

The investigator and qualified designees are responsible for detecting, documenting, and recording events that meet the definition of an AE or SAE and monitoring all reported events, including those reported by the participant.

The method of recording, evaluating, and assessing the causality of AEs and SAEs and the procedures for completing and transmitting SAE reports are provided in Appendix 3 (Section 10.3). The method of reporting AESIs is provided in Section 8.4.7.

8.4.1. Time Period and Frequency for Collecting Information on AEs, SAEs, and AESIs

All AEs, SAEs, and AESIs will be collected from the signing of the ICF until the last follow-up visit at the time points specified in the SoA (Table 1).

Medical occurrences that begin before the start of IMP but after obtaining informed consent will be recorded as non-treatment-emergent AEs; these will not be included in safety analyses.

All SAEs and AESIs will be recorded and reported to the sponsor or designee immediately; under no circumstance should the reporting time exceed 24 hours (Section 10.3.4). The investigator will submit any updated SAE data to the sponsor within 24 hours of it being available.

Investigators are not obligated to actively seek information on AEs or SAEs after conclusion of the study participation. However, if the investigator learns of any SAE, including a death, at any time after a participant has been discharged from the study, and they consider the event to be reasonably related to the IMP or study participation, the investigator must promptly notify the sponsor.

8.4.2. Method of Detecting AEs and SAEs

The method of recording, evaluating, and assessing causality of AE and SAE and the procedures for completing and transmitting SAE reports are described in Section 10.3.

Care will be taken not to introduce bias when detecting AEs and/or SAEs. Open-ended and nonleading verbal questioning of the participant is the preferred method to inquire about AE occurrences.

8.4.3. Follow-up of AEs and SAEs

After the initial AE/SAE report, the investigator is required to proactively follow each participant at subsequent visits/contacts.

All AEs observed from the moment the participant signs the ICF must be followed through resolution until one of the following occurs:

- The participant's last study visit
- The participant is lost to follow-up
- The participant withdraws consent

Resolution means that the participant has returned to a baseline state of health, or the investigator does not expect any further improvement or worsening of the AE.

Every effort should be made to follow all AEs and SAEs that are considered to be related to IMP or study procedures until an outcome can be reported. If the participant is lost to follow-up, all AEs will be categorized based on the investigator's last assessment.

As long as the participant is still in the study, resolution of SAEs (with dates) should be documented on the AE page of the eCRF and in the participant's medical record to facilitate source data verification. If, after follow-up, return to the baseline status or stabilization cannot be established, an explanation should be recorded on the SAE form.

All pregnancies reported during the study should be followed until pregnancy outcome (Section 8.4.6).

For SAEs, AESIs (Section 8.4.7), nonserious AEs, and pregnancies, the sponsor's designee may follow-up by telephone, fax, electronic mail, and/or a monitoring visit to obtain additional case details and outcome information (eg, from hospital discharge summaries, consultant reports, or autopsy reports) to perform an independent medical assessment of the reported case.

Further information on follow-up procedures is provided in Section 10.3.

8.4.4. Reporting of AEs and SAEs

All AEs that occur during the study, from signing of the ICF until the EoTP or the last follow-up visit, are to be recorded on the appropriate AE pages (either "serious" or "nonserious") of the eCRF. The investigator should complete all the details requested, including date of onset, time of onset, stop date (when applicable), stop time (when applicable), severity, action taken, outcome, and relationship to IMP, to corticosteroid (non-IMP) use, and to study procedures. Each event should be recorded separately on the eCRF.

Any SAE, including death due to any cause, which occurs during this study after the signing of the ICF, whether or not related to the IMP, must be reported immediately (within 24 hours of the study site's knowledge of the event). Further information on follow-up procedures is provided in Section 8.4.3 and Section 10.3.

The report will contain as much available information concerning the SAE as possible, to enable the sponsor (or an authorized representative) to file a report, which satisfies regulatory reporting requirements. These timelines apply to initial reports of SAEs and to all follow-up reports.

Criteria for documenting the relationship to IMP and severity, outcome, and action taken will be the same as those previously described.

All SAEs that are spontaneously reported within 30 days after the last study visit are to be collected and reported in the safety database, and all efforts should be made to follow-up until resolution.

Additional follow-up information should be completed and entered on a paper SAE report form and sent by fax/email to the sponsor's designee.

8.4.5. Regulatory Reporting Requirements for SAEs

Prompt notification by the investigator to the sponsor of an SAE is essential so that legal obligations and ethical responsibilities toward the safety of participants and the safety of IMP under clinical investigation are met.

The sponsor has a legal responsibility to notify both the local regulatory authority and other regulatory agencies about the safety of IMP under clinical investigation. The sponsor will comply with country-specific regulatory requirements relating to safety reporting to the regulatory authority, IRBs/IECs, and investigators.

An investigator who receives a safety report describing an SAE or other specific safety information (eg, summary or listing of SAEs) from the sponsor will review and then file it along with the efgartigimod IB and will notify the IRB/IEC, if appropriate according to local requirements.

The sponsor (or designee) is responsible for reporting suspected unexpected serious adverse reactions (SUSARs) to the relevant regulatory authorities and IECs/IRBs per applicable regulatory requirements. The sponsor (or designee) is also responsible to forward SUSAR reports to all investigators involved in the study, who will be required to report these SUSARs to their respective IECs/IRBs, per their local regulatory requirements.

8.4.6. Pregnancy

- If pregnancy is reported, the investigator will record the pregnancy information on the appropriate form and submit it to the sponsor within 24 hours of learning of the pregnancy in the female participant or the female partner of the male participant. Contact details are provided in Serious Adverse Event Reporting.
- The participant and pregnant female partner, if consented (Section 10.1.3), will be followed to determine the outcome of the pregnancy. The investigator will collect follow-up information on the participant/pregnant female partner and the neonate and forward it to the sponsor.
- While pregnancy itself is not considered an AE or SAE, any pregnancy complication
 or elective termination of a pregnancy for medical reasons will be reported as an AE
 or SAE. Abnormal pregnancy outcomes (eg, spontaneous abortion, fetal death,
 stillbirth, congenital anomalies, ectopic pregnancy) are considered SAEs and will be
 reported accordingly.
- Any poststudy pregnancy-related SAE considered reasonably related by the investigator to IMP will be reported to the sponsor as described in Section 8.4.4.

• Any female participant who becomes pregnant during the study will discontinue IMP.

8.4.7. Adverse Events of Special Interest

An AESI is an event of scientific and medical concern specific to the sponsor's product or program. Ongoing monitoring and rapid communication by the investigator to the sponsor or designee could be appropriate. An AESI can be serious or nonserious, related or not related to the IMP or study procedures.

Efgartigimod treatment leads to reduced IgG levels. Because low IgG levels are associated with increased infection risks, events in the MedDRA System Organ Class (SOC) Infections and Infestations are considered AESIs in this study. These events will be reported according to the time frame specified in Section 8.4.1 and Section 10.3.4, with the following information provided:

- Causal pathogen
- Location of infection
- Relationship to an underlying medical condition, medical history, and concomitant medications
- Reoccurrence of a previous infection/infestation
- Any confirmatory procedure, culture, or urgent medical intervention

Participants for whom an AESI has been reported may be temporarily interrupted from IMP treatment as specified in Section 7.1.2.

8.4.7.1. Risk Mitigation for COVID-19 and Other Significant Infections

All candidates with clinically significant active infection that is not sufficiently resolved before baseline in the investigator's opinion, recent surgeries, and/or serious diseases will be excluded from study participation (exclusion criteria 5C, 6A, 9, and 13A). Additionally, IMP administration will be interrupted for any participant who contracts a clinically significant infection during the study; IMP administration will resume when the participant is considered healthy enough receive IMP.

A COVID-19 test is performed at screening if required per local regulations (Table 1); candidates who test positive will be excluded from taking part in the study. Additionally, participants who test positive for COVID-19 or report COVID-19 symptoms at any point during the study will have both IMP administration and site visits interrupted until it is considered safe to resume both (Section 10.14). If a participant contracts COVID-19, the event is recorded and reported as an AESI (Section 8.4.7).

Refer to Section 10.14 for operational considerations for COVID-19 risk mitigation.

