7.1. IMP Discontinuation

7.1.1. Permanent Discontinuation

Permanent discontinuation of IMP occurs when the participant stops receiving IMP before the end of the study, and does not resume receiving IMP. The participant also must not have withdrawn informed consent.

The investigator will document the primary reason for early discontinuation of IMP.

Participants who permanently discontinue IMP will be encouraged to remain in the study and attend mandatory on-site visits as specified in the SoA (Table 1). If the participant cannot attend these visits for any reason, the study site will perform an early study discontinuation (ESD) visit and safety follow-up visits as specified in the SoA (Table 1).

Unless consent from the study has been withdrawn, the participant will attend an early treatment discontinuation (ETD) visit. Study sites will attempt to perform the ETD visit within 7 days after the participant's final IMP administration. After the ETD, the participant will continue participation in the study through the rest of the 36-week treatment period and may receive rescue therapy (defined in Section 6.8.3). At week 36, the participant will complete the EoTP visit assessments (Table 1). If the participant meets rollover eligibility requirements (described in the ARGX-113-2010 protocol) at the end of the EoTP visit, they will be invited to immediately enroll in the OLE study ARGX-113-2010. If the participant does not meet rollover eligibility requirements or chooses not to enroll in the OLE study, they will participate in the 7-week treatment-free follow-up period. Refer to the SoA (Table 1) for data to be collected at the time of discontinuation of IMP and follow-up and for any other evaluations that need to be completed.

The following circumstances will result in the permanent discontinuation of IMP:

- Participant becomes pregnant or intends to become pregnant (refer to Section 8.4.6).
- Investigator decides that discontinuing IMP is in the participant's best interest (the sponsor will be informed).
- Participant develops an SAE or AE that contraindicates further administration of IMP in the investigator's opinion.
- Unblinding occurred.
- Participant exhibits any of the conditions outlined in Section 6.8.3. In these cases, participant may start rescue therapy.
- Any of the liver chemistry criteria resulting in temporary IMP discontinuation outlined in Section 7.1.2 is met, and the event is considered by the investigator to be related to the IMP.

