- The participant develops any of the following, based on the sponsor's determination of relatedness:

- Any treatment-emergent adverse event (TEAE) of Common Terminology Criteria for Adverse Events (CTCAE) severity grade 4 that is considered related to IMP
- Any treatment-emergent SAE of grade 3 considered related to IMP
- Any infections of grade 3 or any serious infection considered related to IMP
- The participant develops any malignancy, either new or recurrent, other than basal cell carcinoma of the skin, regardless of relatedness.

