7.1.2. Temporary Discontinuation

Temporary discontinuation of IMP occurs when the participant discontinues receiving IMP before the end of the study and resumes once the cause for the discontinuation has been resolved.

Reasons for temporary discontinuation may include an AE that meets the following criteria:

- Any SAE considered related to IMP by the sponsor
- Clinically significant active infection considered related to the IMP by the sponsor
- Any of the following liver chemistry laboratory results:
 - Alanine aminotransferase (ALT) or aspartate aminotransferase (AST) values
 >8 times the upper limit of its normal reference range (×ULN)
 - ALT or AST values >5×ULN sustained for more than 2 weeks
 - ALT or AST values >3×ULN plus total bilirubin >2×ULN
 - ALT or AST values >3×ULN plus international normalized ratio (INR) >1.5
 - ALT or AST values >3×ULN with the appearance of any of the following signs and symptoms of liver toxicity:
 - o Fatigue
 - o Nausea
 - Vomiting
 - o Pain or tenderness in the upper-right quadrant of the abdomen
 - Fever
 - o Rash
 - o Eosinophilia (eosinophil count >5×10⁸/L)

Participants with any of these events will have the laboratory tests repeated within 48 hours. These participants will also be evaluated to determine whether the cause of the liver enzyme elevation is a disease/condition other than toxicity related to IMP (eg, viral hepatitis, preexisting or acute liver disease, or toxicity related to concomitant medications other than IMP). If the event is considered by the investigator to be related to the IMP, IMP will be permanently discontinued (Section 7.1.1).

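### Protocol 8.4.7.1 says dosing resumes after any clinically significant infection, but 7.1.1 requires a permanent stop when the infection is related and is grade 3 or serious

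*Protocol*

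**What the plan says.** **Protocol Section 7.1.1 (permanent discontinuation).** Permanent discontinuation means that the participant "stops receiving IMP before the end of the study, and does not resume receiving IMP". The list of triggers is mandatory: "The following circumstances will result in the permanent discontinuation of IMP". One group of triggers opens with "The participant develops any of the following, based on the sponsor's determination of relatedness" and includes "Any infections of grade 3 or any serious infection considered related to IMP".

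**Protocol Section 8.4.7.1 (COVID-19 and other significant infections).** The general rule has two halves. First, "IMP administration will be interrupted for any participant who contracts a clinically significant infection during the study". Second, "IMP administration will resume when the participant is considered healthy enough receive IMP". For a positive COVID-19 test or COVID-19 symptoms, IMP and site visits are "interrupted until it is considered safe to resume both".

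**The sections in between.** Section 8.4.7 makes all infections AESIs and says IMP may be interrupted temporarily, citing 7.1.2. Section 7.1.2 lists related clinically significant infection and any related SAE among the possible reasons for temporary discontinuation. Its one link to the permanent rule closes the paragraph on liver test work-up: "If the event is considered by the investigator to be related to the IMP, IMP will be permanently discontinued (Section 7.1.1".

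**The concern.** Both sections are written as instructions, and they turn on different things. The 7.1.1 stop depends on relatedness as determined by the sponsor, together with grade or seriousness. Resumption under 8.4.7.1 depends only on recovery, and the section does not say who decides that the participant is well enough. A site treating an infection would naturally look in 8.4.7.1, which is titled for that purpose, and nothing there says that some infections rule out further dosing.

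The stake is patient safety. Efgartigimod lowers IgG, and the protocol gives that as the reason infections are AESIs. Section 2.2 names infections among the main causes of death in bullous pemphigoid. If 8.4.7.1 is followed as written, a participant could be dosed again after an infection the sponsor has attributed to IMP, or sites could handle the same event differently.

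**Working it through.** No arithmetic applies. The check is to apply both rules to each type of clinically significant infection.

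| Clinically significant infection | Infection rule in 7.1.1 | Rule in 8.4.7.1 | Can both be followed? |
|---|---|---|---|
| Not related to IMP, any grade | No stop | Interrupt, then resume on recovery | Yes |
| Related, below grade 3 and not serious | No stop | Interrupt, then resume on recovery | Yes |
| Related, and grade 3 or serious | Stop, never resume | Interrupt, then resume on recovery | No |

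Grade 4 infections belong in the third row: Section 10.3.3 treats every grade 4 event as serious, and 7.1.1 also has a separate rule for related grade 4 TEAEs.

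1. **Where the conflict lies.** The interruption half of 8.4.7.1 is compatible with 7.1.1, since dosing can be held while the sponsor assesses relatedness. Only the resumption half conflicts, and only in the third row.
2. **The COVID-19 sentence.** It conflicts only when the COVID-19 case is itself a related grade 3 or serious infection.
3. **Sections 8.4.7 and 7.1.2.** Neither contradicts 7.1.1, because both are permissive about temporary discontinuation. They do not resolve the conflict either. A reader who goes from 8.4.7.1 up to 8.4.7 is sent to 7.1.2, the temporary rule, and the only onward link there concerns liver events.
4. **Cross-references to 7.1.1.** It is cited at the point of use in four places: 6.3.1 (unblinding), 6.8.1.3 (treatment failure), 6.8.3 (rescue conditions) and 7.1.2 (related liver events). It is cited in neither 8.4.7 nor 8.4.7.1, which refers only to the exclusion criteria, Table 1, Section 10.14 and Section 8.4.7.
5. **Precedence.** No statement was found of which section governs. The serious-infection row of Table 2 is cut off in the text available, so it is not relied on in either direction.

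**The case against.** The best counter-argument is that the sections can be reconciled by ordinary reading. Interrupting and resuming is the protocol's vocabulary for temporary discontinuation, and 8.4.7.1 sits under a section that points to 7.1.2. Section 7.1.1 is the dedicated stopping-rule section and its infection trigger is the narrower one, so it should act as the exception to a general rule. Resumption also rests on a judgement of fitness and is not automatic. Safeguards exist: under 7.1.1 the investigator must stop IMP for an event that contraindicates it, and 8.4.1 requires SAEs and AESIs to reach the sponsor within 24 hours. A missing citation proves little by itself, since 8.4.6 tells pregnant participants to stop IMP without citing 7.1.1.

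Much of this stands. The reconciling reading is probably what was intended, the safeguards lower the chance of error, and the citation count is only supporting evidence. None of it settles which rule governs. Section 8.4.7.1 applies to any participant with a clinically significant infection, and the judgement it calls for is about recovery, not about relatedness. The pregnancy section omits a citation but never says dosing will resume; the infection section gives a contrary instruction.

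**Conclusion.** The concern holds. For infections that are clinically significant, judged related by the sponsor, and grade 3 or serious, 7.1.1 forbids further dosing while 8.4.7.1 says dosing resumes on recovery. One sentence of 8.4.7.1 conflicts directly with one trigger in 7.1.1; the COVID-19 sentence conflicts only within that same subset.

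The frequency cannot be stated, because the documents give no rate of related grade 3 or serious infections. The conclusion rests on the current protocol wording and assumes nothing about how sites behave. The protocol should be changed because a safety rule followed as written could lead to the wrong action.

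**What to change.** State that Section 7.1.1 governs:

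- In 8.4.7.1, add to the general resumption sentence: *unless the criteria for permanent discontinuation in Section 7.1.1 are met*. Add the same clause to the COVID-19 sentence for consistency.
- In 8.4.7, cite Section 7.1.1 next to Section 7.1.2.
- Optionally, limit the first two bullets of 7.1.2 (related SAEs and related infections) to events that do not meet 7.1.1.

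The required change is one clause in two sentences and one added cross-reference.
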